This is a non-randomised controlled trial with three arms, comparing older people with mild to moderately severe depressive symptoms receiving modified MBCT led by a mindfulness teacher, MBCT led by social workers, and care as usual.

Participants

Participants will be recruited from District Elderly Community Centres (DECC) and Integrated Community Centre for Mental Wellness (ICCMW). We aimed to recruit 32 participants for each arm, totaling 96 participants in the study. They will be included if they are aged (1) 60 years or older, (2) have depressive symptoms of mild level or above, as indicated by scoring 5 or more in PHQ-9, and (3) can give informed consent to participate. The exclusion criteria are (1) known history of autism, intellectual disability, schizophrenia-spectrum disorder, bipolar disorder, Parkinson's disease, or dementia, (2) imminent suicidal risk, and (3) difficulty in communication.

Intervention

The MBCT protocol has been modified according to our pilot test with older people with depressive symptoms and suggestions from existing literature in teaching mindfulness to the older population. It consists of eight 2-hour weekly sessions, but the whole day retreat is excluded. Each session contains guided mindfulness exercises, feedback and discussion,

homework review, and psychoeducation. The programme is conducted in Cantonese and led by either a MBCT teacher who received formal training organized by the Oxford Mindfulness Centre and the Hong Kong Centre for Mindfulness or a social worker supervised by the MBCT teacher. The care as usual group received usual service provided in DECC and ICCMW.

Outcomes

Demographic information will be collected at baseline. All outcome measures will be collected at baseline (T0), 8-week (T1: immediately after the intervention), and 12-week (T2). The questionnaires are self-administered but trained social workers or research assistants will provide support in completing the questionnaire when needed. The questionnaire is expected to last for roughly 30 minutes.

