Baseline demographic information and outcome measures among the three groups will be compared using independent sample t-test. Mixed ANOVA will be used to compare outcome changes from T0 to T2 among the groups. Post-hoc analyses, such as pairwise comparisons, will be performed to identify groups with significant changes. All results will be reported with appropriate effect sizes, statistical significances, and confidence intervals. If the findings demonstrate intervention effects, a regression model will be conducted to examine whether psychological flexibility (change scores) are associated with lower depressive symptoms post intervention, while controlling for baseline depression.

References

- Geiger, P. J., Boggero, I. A., Brake, C. A., Caldera, C. A., Combs, H. L., Peters, J. R., & Baer, R. A. (2016). Mindfulness-Based Interventions for Older Adults: a Review of the Effects on Physical and Emotional Well-Being. *Mindfulness*, *7*(2), 296–307. <https://doi.org/10.1007/s12671-015-0444-1>
- Morris, J. (2019). *Development and validation of a short form of the Comprehensive assessment of Acceptance and Commitment Therapy processes (CompACT-SF)*. University of Nottingham.
- Ng, S. (2013). Validation of the 10-item Chinese perceived stress scale in elderly service workers: one-factor versus two-factor structure. *BMC Psychology*, *1*(1), 9. <https://doi.org/10.1186/2050-7283-1-9>
- Segal, Z. V., Williams, J. M. G., & Teasdale, J. D. (2012). *Mindfulness-based cognitive therapy for depression*. Guilford Press.
- Shih, V. W., Chan, W.-C., Tai, O.-K., Wong, H.-L., Cheng, C. P., & Wong, C. S. (2021). Mindfulness-Based Cognitive Therapy for Late-Life Depression: a Randomised Controlled Trial. *East Asian Archives of Psychiatry*, *31*(2), 27–35. <https://doi.org/10.12809/eaap2075>
- Sun, W. J., Xu, L., Chan, W. M., Lam, T. H., & Schooling, C. M. (2012). Depressive symptoms and suicide in 56,000 older Chinese: a Hong Kong cohort study. *Social Psychiatry and Psychiatric Epidemiology*, *47*(4), 505–514. <https://doi.org/10.1007/s00127-011-0362-z>

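### No analysis set or missing-data method is stated, and a conventional mixed ANOVA would by default analyse completers only

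*Combined protocol and SAP*

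**What the plan says.** The analysis plan is one paragraph under Data analysis. It lists baseline t-tests, then states: "Mixed ANOVA will be used to compare outcome changes from T0 to T2 among the groups". Next comes "Post-hoc analyses, such as pairwise comparisons, will be performed to identify groups with significant changes", a promise that "All results will be reported with appropriate effect sizes, statistical significances, and confidence intervals", and a mechanism analysis that depends on the earlier result: "If the findings demonstrate intervention effects, a regression model will be conducted". That regression uses change in psychological flexibility and post-intervention depression, so it also needs follow-up data.

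The Design section says "This is a non-randomised controlled trial with three arms", and the Participants section gives the size: "We aimed to recruit 32 participants for each arm, totaling 96 participants in the study". The Outcomes section schedules every measure at baseline (T0), 8 weeks (T1) and 12 weeks (T2).

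No section says who is analysed (all enrolled, completers or session attenders), how missed assessments are handled, what dropout is expected, or what sensitivity analysis will be done.

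**The concern.** Complete-case analysis is not a rule the plan states. It is what conventional mixed ANOVA does unless told otherwise, because each person must have a value at every level of the time factor.

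The phrase about T0 to T2 can be read in two ways:

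- **Three time levels** (likelier, since T1 is collected). Anyone missing T1 or T2 is dropped, and the scores they did give are lost.
- **Two time levels.** T1 is unused for everyone, and anyone missing T2 is still dropped.

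Arm-dependent dropout is plausible. The MBCT arms attend eight weekly two-hour sessions with homework, while the comparator receives its usual service, so reasons for missing T1 or T2 may differ. Allocation is not randomised, so deletion can add to existing imbalance. With no analysis set named, whether people who stopped attending count could be decided after the data are seen.

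The pairwise comparisons serve the first two objectives, and the mechanism regression runs only if effects appear. A distorted main contrast would carry into both, and nothing in the plan would show its direction.

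**Working it through.** **Inputs from the documents.** 32 per arm; 32 x 3 = 96, which agrees with the stated total. Three visits. The basis for 32 cannot be reproduced, since alpha, power, effect size, SD and dropout are not given.

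**Assumptions (not in the documents).** Normally distributed scores with SD 5, correlation 0.5 between any two visits, true MBCT-minus-usual-care change of -2.0 at T1 and T2, and no mean change in usual care. Dropout rates are illustrative.

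**1. Data lost, three-level reading.** People with T1 = 32 x (1 - a); completers = 32 x (1 - a)(1 - b), where a is lost by T1 and b is the share of the rest lost by T2.

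| Loss (a + b) | With T1, per arm | Completers, per arm | T1 seen but dropped, of 96 |
|---|---|---|---|
| 5% + 5% | 30.4 | 28.9 | 4.6 |
| 10% + 10% | 28.8 | 25.9 | 8.6 |
| 15% + 10% | 27.2 | 24.5 | 8.2 |

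The two readings differ when people miss T1 but return. If 5% of the 25.9 seen at T2 had missed T1, the three-level reading analyses 24.6 per arm and the two-level reading 25.9, a difference of 3.9 people over three arms.

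**2. Precision under random loss of 10% + 10%.** SD of change = 5 x sqrt(2 x (1 - 0.5)) = 5. Completer SE of the change contrast = 5 x sqrt(2/25.9) = 1.39. For a mixed model, add the information from the three patterns in each arm (T0 only: 32 - 28.8 = 3.2; T0 and T1: 28.8 - 25.9 = 2.9; all three: 25.9), with the covariance treated as known, and invert. The SE is 1.30 at T1 and 1.35 at T2. The precision gain, (completer SE / model SE) squared minus 1, is 14.0% at T1 and 5.9% at T2. It is 6.6% and 2.9% at 5% + 5%, and 15.4% and 7.2% at 15% + 10%.

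**3. Bias.** Simulation with 3 million per arm. T1 is always seen. T2 is lost with one probability if the person had not improved at T1 and 10% if they had. An arm without this rule loses 15% at random. Completer effects, T1 / T2 (truth -2.00):

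| Rule applies in | 35% vs 10% | 25% vs 10% |
|---|---|---|
| MBCT only | -2.56 / -2.28 | -2.33 / -2.17 |
| Both arms | -1.93 / -1.96 | -1.96 / -1.98 |
| Usual care only | -1.36 / -1.69 | -1.63 / -1.82 |

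Random loss in both arms gives -2.00 / -2.00. The likelihood estimate is -1.99 to -2.01 in all these cases, where loss depends only on observed scores.

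With the rule in one arm, T2 bias over SE runs from 0.17/1.39 = 0.12 to 0.31/1.39 = 0.22. T1 bias runs from 0.33/1.39 = 0.24 to 0.64/1.39 = 0.46.

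**4. A second simulation with different settings.** It used 300,000 per arm, SD 5, correlations of 0.5 (T0 with T1), 0.6 (T1 with T2) and 0.5 (T0 with T2), and T2 dropout logistic in the T1 score. When the rate or mechanism differed by arm, with 20-30% dropout in at least one arm, completer T2 bias was about 0.05 to 0.26 points. The estimate from all observed data was within 0.02 of the truth.

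**5. What a likelihood model does not repair.** If T1 and T2 are both lost according to the unseen T1 change, the likelihood T1 / T2 estimates are -2.43 / -2.14 (MBCT only) and -1.51 / -1.84 (usual care only) under 35% vs 10%. Under 25% vs 10% they are -2.24 / -2.08 and -1.73 / -1.91. When dropout followed the unseen T2 score in the second simulation and differed by arm, both methods were biased: completers by about 0.2 to 1.25 points, the all-data estimate by about 0.3 to 1.6.

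**The case against.** The strongest reply is that the harm rests on facts the documents do not supply. Listwise deletion is inferred from convention, and no dropout rate or SD is given. On the T0-to-T2 change the effect is small even in the adverse scenarios: 0.17 to 0.31 points with the rule in one arm, 0.02 to 0.04 with it in both, and a precision gain of about 3 to 7%. The larger figures belong to T1, which the plan does not single out. The adverse cases need outcome-driven loss in one arm and random loss in the other, and nothing in the documents establishes that. The precision gain is a best case, since the covariance would have to be estimated from at most 96 people. Unadjusted confounding from non-random allocation may matter more, and naming an analysis set with imputation before the ANOVA would be enough.

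Most of this stands as a limit on size. It does not remove the point: the plan still does not say who is analysed or what happens to incomplete cases. Replacing the ANOVA is one route, and imputation is an acceptable alternative. It is also true that no model reveals the direction of bias when loss depends on unseen values; only dropout reporting and sensitivity analyses inform that.

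**Conclusion.** The concern holds. The omission is certain from the text; its consequences are conditional. Under the illustrative rates, about 5 to 9 of 96 people would give T1 data that a three-level completer analysis discards. Under the assumed SD, correlation and effect, one-arm outcome-dependent loss biases the T2 contrast by 0.1 to 0.2 standard errors and the T1 contrast by 0.2 to 0.5, in either direction. Bias is nil under completely random loss and near nil when the same rule acts in both arms. This should be corrected before analysis because a concrete alternative uses all observed data and removes the bias under missing-at-random. It is not a flaw that by itself would overturn the trial's conclusions.

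**What to change.** - **Analysis set.** Include every enrolled participant in the arm joined, whatever the number of sessions attended. Those with T0 only stay in.
- **Main model.** Replace the mixed ANOVA with a REML linear mixed model for repeated measures. Use T0, T1 and T2 as responses, an unstructured covariance, and fixed effects for group, time and group-by-time. Report change contrasts at T1 and T2. A small-sample degrees-of-freedom correction such as Kenward-Roger is sensible at this size.
- **Keep T0 as a response.** This preserves the planned change contrast. Adjusting for T0 targets a different one when arms differ at baseline. With a true change difference of -2.0 and correlation 0.5, it gives (2 - 2) - 0.5 x 2 = -1.0 if MBCT starts 2 points higher, and (-2 - 2) + 0.5 x 2 = -3.0 if it starts 2 points lower.
- **State the limits.** The model is valid under missing-at-random. It does not remove missing-not-at-random bias or confounding from non-random allocation.
- **Reporting and sensitivity.** Report dropout by arm and visit. Give completer results, and an imputation with arm-specific delta shifts fixed in advance.
- **Alternative.** Multiple imputation before the planned ANOVA, on the same analysis set, would also close the gap.

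The cost is slightly more analysis work: a different model and two sensitivity analyses. Data and visits are unchanged.

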Mindfulness-based interventions, such as mindfulness-based cognitive therapy (MBCT), have the potential in improving psychological health in older people. MBCT is a group intervention originally designed to prevent recurrent depressive disorders (Segal et al., 2012). It combines mindfulness practices and cognitive-behavioural elements to enhance an individual's understanding of the interacting relationships among thoughts, emotions, bodily sensations, and behaviours. Mindfulness practice emphasizes on developing a moment-to-moment, non-judgmental awareness and may be helpful in alleviating depression by directing individual's attention to the present instead of ruminating in the past. Systematic reviews have shown the efficacy of MBCT in reducing depression, anxiety, loneliness, stress, sleep problems, ruminations, general mood, and positive affect (Geiger et al., 2016; Thomas et al., 2020). However, over half of the included studies lacked a control group and mixed findings were observed possibly because of inconsistent modifications to the protocol, methodological flaws, and study limitations.

The application of MBCT in the Chinese older population is understudied. Recently, a randomized controlled trial on MBCT for older people were conducted in Hong Kong. Shih et al. (2021) compared a standard MBCT to an active control group (physical exercise + health education) for older people with depression and revealed that, while both groups showed a reduction in the severity of depressive symptoms, only the MBCT group showed improvement in mindfulness.

With these promising findings, more studies are needed to establish the evidence base for the intervention and inform clinical practice in this population. We aim to explore whether a modified MBCT based on older people's feedback can reduce depressive symptoms and

improve mindfulness. With the growing older people population, there is a need for greater social welfare capacity to promote their well-being, we also examine whether a modified MBCT led by social workers under the supervision of a mindfulness teacher can benefit the population.

Objectives

- To evaluate the effectiveness of MBCT in improving mental health and mindfulness in older people with depressive symptoms as compared to care as usual
- To compare the effectiveness between MBCT led by mindfulness teacher and that led by social workers
- To examine psychological flexibility as a potential mechanism of change

Methods

Design

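### The only regression for the mechanism objective has no arm term and no stated analysis set; pooled over the three arms, it can show an association when flexibility and depression are unconnected

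*Combined protocol and SAP*

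**What the plan says.** The Objectives section lists as its third aim "To examine psychological flexibility as a potential mechanism of change". The only analysis that links flexibility to depression is the last sentence of Data analysis, whose stated question is "whether psychological flexibility (change scores) are associated with lower depressive symptoms post intervention, while controlling for baseline depression". Baseline depression is the one covariate named. The same sentence makes the analysis conditional on an earlier result: "If the findings demonstrate intervention effects, a regression model will be conducted". Nothing in the document says whether the model uses all three arms together, the two MBCT arms, or each arm separately.

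The Design section states "This is a non-randomised controlled trial with three arms"; two of the arms receive MBCT and one receives care as usual. The group analysis is separate ("Mixed ANOVA will be used to compare outcome changes from T0 to T2 among the groups") and does not relate one score to the other. Under Outcomes, every measure is taken at T0, T1 (straight after the programme, week 8) and T2 (week 12). Post-intervention PHQ-9 therefore points to T1, but the window for the CompACT-8 change score is not written out.

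**The concern.** Arm can influence both variables in the regression. If MBCT raises flexibility and lowers depressive symptoms by separate routes, MBCT participants tend to have larger flexibility gains and lower PHQ-9 scores than care-as-usual participants. A pooled model without arm reads that contrast as an association between the two scores. Baseline PHQ-9 does not block this route, because the effect of arm arises after baseline.

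The opening condition makes this worse. The regression is run only when intervention effects have been found, which is when arm is most likely to be acting on the scores. A significant coefficient could then be reported in support of the mechanism objective although it only restates the treatment effect.

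**Working it through.** **Inputs from the document.** Three arms, two of them MBCT; "We aimed to recruit 32 participants for each arm, totaling 96 participants in the study". The sum agrees: 3 × 32 = 96. No SD, correlation or expected effect is given, so everything below except the arm size is an assumption.

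**Assumed set-up.** Scores are in SD units. T0 and T1 values of each score correlate at r = 0.3, 0.5 or 0.7. Both MBCT arms raise T1 CompACT-8 and lower T1 PHQ-9 by d. Residuals are independent and there is no path from flexibility to depression, so the true slope is 0.

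**Expected slope without arm.** With two of three arms on MBCT, the MBCT indicator has variance (2/3)(1/3) = 2/9. The covariance that arm induces between flexibility change and T1 PHQ-9 is −(2/9)d². The within-arm variance of the change score is 2(1 − r). Hence

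slope = −(2/9)d² / [2(1 − r) + (2/9)d²].

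- d = 0.5: (2/9)(0.25) = 0.0556. At r = 0.5 the slope is −0.0556/1.0556 = −0.053; at r = 0.3, −0.0556/1.4556 = −0.038; at r = 0.7, −0.0556/0.6556 = −0.085.
- d = 0.8: (2/9)(0.64) = 0.1422. At r = 0.5 the slope is −0.1422/1.1422 = −0.125; at r = 0.3, −0.1422/1.5422 = −0.092; at r = 0.7, −0.1422/0.7422 = −0.192.

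Simulated mean slopes agree: −0.040 / −0.055 / −0.084 at d = 0.5 and −0.092 / −0.127 / −0.194 at d = 0.8 (r = 0.3 / 0.5 / 0.7). With arm added they are within 0.002 of 0.

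**False-positive rate.** Two-sided 5% test, 5,000 simulated trials per cell, r = 0.3 / 0.5 / 0.7:

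| MBCT effect on both scores | Pooled, no arm | Pooled, two arm indicators |
|---|---|---|
| 0.3 SD | 5.4 / 6.5 / 6.4% | 4.7 / 5.5 / 5.1% |
| 0.5 SD | 7.7 / 9.2 / 13.3% | 5.1 / 4.9 / 5.3% |
| 0.8 SD | 18.1 / 28.0 / 52.0% | 4.9 / 5.2 / 5.3% |

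**Boundary cases.**
- No MBCT effect: 4.7-4.8% without arm.
- 0.8 SD on one score only, r = 0.5: 5.2%.
- 0.8 SD on one score and 0.3 SD on the other: 8.3-8.6%.
- MBCT participants only, equal effects in the two MBCT arms: 4.7-5.4%.
- MBCT participants only, social-worker-led effect half the teacher-led effect: 4.9 / 5.1 / 5.4% for a teacher-led effect of 0.5 SD and 5.6 / 6.0 / 7.8% for 0.8 SD. A leader indicator brings these to 4.4-5.1%.

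**Effect of the opening condition.** This was checked under a second data model (effects in residual SDs, baseline slope 0.5), counting only significant results in the favourable direction, where the nominal rate is 2.5%. Without the condition, the pooled model gives 7.2% at 0.5 SD and 22.4% at 0.8 SD. Run only after a significant MBCT effect on PHQ-9, it gives 9.1% and 23.2%. With arm, both are 2.7-2.8%.

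**The case against.** The strongest reply is that the harm is conditional. It needs pooling, which the plan does not state, and a sizeable effect on both scores. The 52% figure sits in one corner of assumed inputs. The authors may intend to use MBCT participants only, and they write of association and of a potential mechanism, not of mediation. All of this stands, and it limits the claim. It does not remove it: the plan leaves the pooled reading open and gives no expected effects that would rule out the larger ones. Nor is an MBCT-only analysis fully free of the problem if the two MBCT arms differ, which the second objective sets out to learn ("To compare the effectiveness between MBCT led by mindfulness teacher and that led by social workers").

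The second reply is that the table flatters the arm-adjusted model by assuming independent residuals. Two self-reports from the same visit probably share mood and response style. With no path, d = 0.5 and a residual correlation of −0.2 (assumed), the planned model rejects in 47 / 61 / 72% of trials and the arm-adjusted model still rejects in 31 / 39 / 43%. At −0.3 and r = 0.5, adding arm only moves the mean slope from −0.265 to −0.223. This stands as well. Arm removes the part of the association that arm induces and nothing more, so the coefficient should not be read as evidence of a mechanism even after the fix.

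Third, arm costs power. It does; the figures are given with the fix.

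**Conclusion.** The concern holds. The plan names a model for a stated objective whose coefficient, if the arms are pooled, mixes the treatment effect on both scores with the within-arm association of interest. The confidence is high for the omission and the direction of the bias. The size in this trial is unknown: negligible at 0.3 SD, a rejection rate of roughly 8-13% at 0.5 SD and 18-52% at 0.8 SD, under the assumptions of no true path, equal MBCT effects on both scores and independent residuals. The change should be made, but the first two objectives do not depend on it.

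**What to change.** In Data analysis, state which participants enter the regression.

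- If all three arms are pooled, add two arm indicators.
- If only MBCT participants are used, add one indicator for who led the group.
- Define the predictor as the T0-T1 change in CompACT-8 and the outcome as T1 PHQ-9.
- Report the coefficient as an exploratory association, noting that shared mood or reverse causation can produce it whatever the covariates.

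Baseline CompACT-8 as a covariate, a lagged model for T2 PHQ-9 and a bootstrap indirect effect are optional sensitivity analyses.

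The cost is one line of text, no new data and some power. Take an assumed true path of 0.3 in size (greater flexibility, lower PHQ-9), at r = 0.3 / 0.5 / 0.7. Where arm has no separate effect on PHQ-9, so that the planned model is unbiased, power goes from 94.8 / 92.1 / 89.9% to 93.6 / 90.2 / 86.5%, a loss of 1.2 / 1.9 / 3.4 points. With separate arm effects of 0.5 SD it goes from 97.7 / 97.0 / 97.8% to 93.7 / 90.0 / 85.5%, a fall of 4.0 / 7.0 / 12.3 points. Part of that fall is bias being removed: at r = 0.5 the planned slope averages 0.35 in size against a true 0.30, and the arm-adjusted slope averages 0.30. Restricting to MBCT participants costs more power, about 75% against 89% for the pooled model with arm in that same r = 0.5 case.
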